8.4.2.2 Methods for Secondary Endpoint

The distribution of PFS will be compared in two randomized arms using a two-sided, log-rank test stratified by the stratification factors as described in Section 3.1. The HR and the corresponding two-sided 95% CI will be estimated in a stratified Cox proportional hazards model using randomized arm as a single covariate. The PFS curves for each randomized arm will be estimated using the KM product-limit method. Two-sided, 95% confidence intervals for median PFS will be computed by Brookmeyer and Crowley method (using a log-log transformation).

ORR in two randomized arms will be compared using a two-sided CMH test, stratified by the same factors. An associated odds ratio and 95% CI will also be calculated. Rates and their corresponding 95% exact CI will be calculated by Clopper-Pearson method for each randomized arm.

The estimation of DOR and TTR in two randomized arms will be computed for subjects who achieve PR or CR using KM product-limit method. Median values of duration and time-to, along with two-sided 95% CI, will be calculated.

8.4.3 Safety Analyses

The safety analysis will be performed in all treated subjects. Descriptive statistics of safety will be presented using NCI CTCAE version 4.0 by treatment arm. All on-treatment AEs, drug-related AEs, late-emergent drug-related AEs, SAEs and drug-related SAEs will be tabulated using worst grade per NCI CTCAE version 4.0 criteria by system organ class and preferred term. On-study lab parameters including hematology, coagulation, chemistry, liver function and renal function will be summarized using worst grade per NCI CTCAE v 4.0 criteria.

8.4.4 Pharmacokinetic Analyses

The concentration vs time data obtained in this study may be combined with data from other studies in the clinical development program to develop a population PK model. This model may be used to evaluate the effects of intrinsic and extrinsic covariates on the PK of nivolumab and to

determine measures of individual exposure (such as steady-state peak, trough, and time-averaged concentration). Model determined exposures may be used for exposure-response analyses of selected efficacy and safety end points. Results of population PK and exposure-response analyses will be reported separately.

8.4.5 Biomarker Analyses

8.4.5.1 Pharmacodynamic Analyses

To assess pharmacodynamic effects in serum obtained from subjects on each treatment arm, summary statistics for biomarkers of [REDACTED] and their corresponding changes (or percent changes) from baseline will be tabulated by planned study visit. In addition, the time course of biomarker outcomes will be investigated graphically. If there is indication of a meaningful pattern across time, further analysis may be completed to characterize the relationship. Possible associations between changes in biomarker measures of interest and exposure to study drug will be explored graphic.

8.4.5.2 Pharmacogenomic Analyses

Pharmacogenomic and Exploratory Analyses

Potential relationships between biomarker data and efficacy or safety endpoints will be investigated as part of an analysis plan aimed at identifying baseline biomarkers that may be used to prospectively identify subjects likely (or not likely) to respond to nivolumab and to identify subjects who may be predisposed to having adverse reactions to treatment. These exploratory predictive biomarker analyses will be completed with biomarkers measured in blood and in tumor samples and will focus primarily--as outlined in the exploratory objectives--on SNPs in select genes associated with immunity or on the expression of [REDACTED], PD-L1, [REDACTED] proteins in tumor specimens. Similar analyses will be completed with data regarding [REDACTED] and putative additional analyses to be completed using FFPE tissue.

Associations between biomarkers and efficacy measures will be analyzed on all randomized subjects with available biomarker data. Efficacy measures will include response, PFS, and OS. Demographic and case-history factors will be examined to determine whether stratification or adjustments should be made within the subsequent statistical analyses, and if necessary, the appropriate stratification or adjustment will be made.

Biomarkers will be summarized graphically as they relate to efficacy and safety endpoints, as applicable. Summary statistics will be tabulated. SNP allele frequencies will be summarized. The relationships between binary measures (eg, response) and candidate biomarkers will be investigated using logistic regression. Associations will be summarized in terms of point and interval estimates of hazard ratios, odds ratios, or other statistics, as appropriate for the analyses completed. Models to predict clinical activity based on combinations of biomarkers may also be investigated.

Additional post hoc statistical analyses not specified in the protocol, such as alternative modeling approaches may be completed. All analyses described in this section are based on the availability of the data.

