The role of PD-L1 as a potential predictive biomarker in SCLC is unknown. Preliminary internal data from SCLC tumor samples show that less than 10% of tumor samples have $\geq 5\%$ PD-L1 positive tumor cells. A preliminary analysis of tumor samples in Study CA209032 showed no suggestion of a correlation of PD-L1 expression and tumor shrinkage under nivolumab therapy. Recently, expression of PD-L1 was shown to be positively correlated with a LD stage, and to be an independently predictive factor of a favorable overall survival versus PD-L1-negative tumors.²⁰

In order to more thoroughly assess the role of PD-L1 protein expression as a predictive biomarker in SCLC, archival or recent tumor tissue will be collected prospectively from all randomized subjects in this study, and a retrospective analysis of efficacy by PD-L1 expression status will be conducted. Subjects enrolled to CA209331 will not be selected or stratified by PD-L1 expression status. However, based on preliminary PD-L1 prevalence estimates in SCLC a reasonable number of PD-L1 positive subjects are anticipated to accrue to each treatment arm for an exploratory analysis.

In addition, tumor mutational burden will be evaluated as an independent predictive biomarker for efficacy, following recently presented data from the CA209032 SCLC cohort,²¹ as part of the exploratory analyses.

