1.3.3 Exploratory Objectives

The exploratory objectives are:

- To evaluate the safety and tolerability of nivolumab versus chemotherapy
- To characterize pharmacokinetics of nivolumab and explore exposure response (exposure-safety and exposure-efficacy) relationships with respect to selected safety and efficacy endpoints
- To explore PD-L1 expression as an independent predictive biomarker for OS, ORR, or PFS in nivolumab and chemotherapy groups
- To explore tumor mutational burden expression as an independent predictive biomarker for efficacy in nivolumab and chemotherapy groups
- To correlate potential predictive biomarkers in peripheral blood and tumor specimens, including proteins involved in regulating immune responses (eg, [REDACTED], PD-L1, [REDACTED]), mutational as well as immunohistochemistry (IHC) spectrum, with endpoints such as ORR, PFS and OS in nivolumab and chemotherapy groups

- [REDACTED]

- To characterize immunogenicity of nivolumab
- To evaluate the proportion of subjects with meaningful symptom deterioration by 12 weeks and by 24 weeks, as measured using the Lung Cancer Symptom Scale (LCSS) average symptom burden index (ASBI), between nivolumab and chemotherapy groups
- To evaluate the time to symptom deterioration (TTSD), as measured by the average symptom burden index (ASBI) of the Lung Cancer Symptom Scale (LCSS), in subjects receiving nivolumab versus chemotherapy
- To assess the subject's overall health status using the EQ-5D index and visual analog scale in nivolumab and chemotherapy groups.

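### Protocol 8.4.5.2 seeks markers that predict response to nivolumab but names only marker-outcome associations, which cannot by themselves separate a predictive marker from a prognostic one

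*Protocol*

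**What the plan says.** The aim is prediction. Protocol 1.3.3 lists as an objective: "To explore PD-L1 expression as an independent predictive biomarker for OS, ORR, or PFS in nivolumab and chemotherapy groups". Protocol 8.4.5.2 describes its work as "identifying baseline biomarkers that may be used to prospectively identify subjects likely (or not likely) to respond to nivolumab". Its readable text names SNPs and PD-L1; other marker names are redacted.

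The methods named in 8.4.5.2 are these:

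- Analysis set: "Associations between biomarkers and efficacy measures will be analyzed on all randomized subjects with available biomarker data". The efficacy measures are response, PFS and OS.
- Model: "The relationships between binary measures (eg, response) and candidate biomarkers will be investigated using logistic regression". Results are to be given as hazard ratios, odds ratios or similar, with interval estimates.
- Adjustment: "Demographic and case-history factors will be examined to determine whether stratification or adjustments should be made within the subsequent statistical analyses". Treatment arm is not mentioned.
- Open clause: "Additional post hoc statistical analyses not specified in the protocol, such as alternative modeling approaches may be completed".

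Protocol 1.1.8 separately plans a retrospective look at efficacy by PD-L1 status. It names no model for it. The forest-plot subgroups for OS in SAP 7.5.1.3 include no biomarker. SAP 7.8.1.3 has a readable heading on TMB and efficacy, but its text is redacted.

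**The concern.** In a randomized two-arm trial, a marker is predictive if the nivolumab-versus-chemotherapy effect changes with the marker. It is prognostic if it is related to outcome whatever the treatment. A regression of outcome on marker tests the second question. The sentences in 8.4.5.2 describe that regression, while the objective asks the first question.

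The protocol itself shows how easily the two are confused. Section 1.1.8 cites a published study in which PD-L1 was associated with limited-stage disease and was an "independently predictive factor of a favorable overall survival versus PD-L1-negative tumors". No treatment contrast is cited, so this is evidence of prognosis described with the word for prediction. The same section reports no sign, in preliminary CA209032 data, that PD-L1 is related to tumor shrinkage on nivolumab.

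At stake is the label put on a marker. The stated use is prospective identification of patients for nivolumab. A marker that is equally favorable on chemotherapy would be no guide to that choice.

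**Working it through.** **1. The plan's own figure.** The only power statement concerns OS: 90% with 482 events and an average HR of 0.745. Check: √482 / 2 × |ln 0.745| = 3.231, and Φ(3.231 − 1.960) = 0.898. It reproduces. The plan gives no operating figure for the biomarker analyses, so the steps below are illustrations.

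**2. Inputs.**

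- From the protocol: 560 subjects, 1:1 (8.1); response rates of 15% on nivolumab and 16.9% on topotecan (1.1.3.5), mean 15.95%; fewer than 10% of samples PD-L1 positive at the 5% cut-off (1.1.8).
- Assumed: two-sided 0.05; marker prevalence p of 5%, 10%, 30% or 50%; marker data on everyone unless stated; a purely prognostic marker, with the same odds ratio (OR) in both arms.

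**3. Pooled association.** The response rates r0 (marker-negative) and r1 (marker-positive) are set so that the overall rate is 15.95%. Then

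SE² = 1/[n(1−p)·r0(1−r0)] + 1/[n·p·r1(1−r1)], and the chance of p < 0.05 is Φ(ln OR / SE − 1.960), plus a negligible opposite tail.

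Example, p = 10% and OR 2: r0 = 0.1485 and r1 = 0.2586. SE² = 1/63.7 + 1/10.74 = 0.1088, so SE = 0.330. 0.693 / 0.330 = 2.10, and Φ(0.14) = 0.556.

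| Prevalence | OR 1.5 | OR 2 |
|---|---|---|
| 5% | 13.7% | 34.5% |
| 10% | 21.4% | 55.6% |
| 30% | 39.0% | 83.2% |
| 50% | 41.1% | 82.6% |

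Simulated logistic regressions (1,000 trials per setting) at 10%, 30% and 50% prevalence agree: 20%, 39% and 42% at OR 1.5; 54%, 80% and 84% at OR 2. If only 60% of subjects have marker data (assumed), the OR 2 figures fall to 37%, 62% and 61%.

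**4. OS association.** With 482 events, the test statistic has mean √(482·p(1−p)) × |ln HR|. A prognostic HR of 0.8 gives 31%, 61% and 69% at 10%, 30% and 50% prevalence.

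**5. Arm-by-arm association.** In the same simulations, the nivolumab arm alone is significant in 12-21% of trials at OR 1.5 and 32-56% at OR 2. The result that looks predictive, significant on nivolumab but not on chemotherapy, occurs in 8-24% of trials for OR 1.5 to 3, although the marker effect is identical in the two arms.

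**6. Interaction test.** With treatment, marker and treatment-by-marker in the logistic model, a purely prognostic marker is flagged in 3-6% of simulated trials at every setting (prevalence 10-50%, OR 1 to 3). At 5% prevalence this was not simulated. There would be only 280 × 0.05 = 14 marker-positive subjects per arm, so every large-sample figure at that prevalence is rough.

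**7. Cost in power.** Take a marker with OR 3 on nivolumab and 1 on chemotherapy. SE² is the sum of the two arms' variances, with n = 280 each. At p = 10%: 0.2007 + 0.2826 = 0.4833, so SE = 0.695. 1.099 / 0.695 = 1.58, and Φ(−0.38) = 0.352. At 5%, 30% and 50% the same formula gives 21%, 62% and 62%.

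**The case against.** The strongest reply is that the text is thin rather than wrong. The sentence on the analysis set defines who is included; it does not say that the arms are pooled, and the objectives, which refer to both treatment groups, fit an arm-by-arm analysis. Section 1.1.8 plans efficacy by PD-L1 status and expects a reasonable number of PD-L1 positive subjects in each arm, which most naturally means comparing the arms within marker levels. Section 8.4.5.2 leaves room for other models. Everything here is exploratory.

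Much of this stands. A reader might infer that the control arm goes unused for the predictive question; Section 1.1.8 does not support that. A reader might also infer that a prognostic marker will usually be reported as predictive. The documents do not support that either: they give no threshold or rule for declaring a marker predictive, results are promised as estimates with intervals, and the rates above are below one half at OR 1.5 throughout and at OR 2 with 5% prevalence.

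What does not stand is that these points close the gap. Section 1.1.8 names no model, no interaction and no marker other than PD-L1 for that analysis. The open clause is optional and post hoc. Arm-by-arm testing does not compare the arms (step 5).

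**Conclusion.** The point holds in a limited form. The readable text of 8.4.5.2 states a predictive aim and names methods that, pooled or by arm, cannot alone establish prediction. For a marker with no predictive effect, pooled association with response is significant in roughly 14-41% of trials at OR 1.5 and 34-83% at OR 2, against about 5% for an interaction test. These figures rest on assumed prevalence (5-50%), assumed prognostic strength and complete marker data, and they are rates of significance, not of misreporting.

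It is tempting to extend the point to TMB, since 1.3.3 gives it the same predictive objective. The documents do not support that: the readable text of 8.4.5.2 does not name TMB, and the SAP text on TMB and efficacy is redacted. Redacted SAP text could also specify an interaction model for other markers; in that case only the protocol wording needs aligning. The consequence is confined to exploratory biomarker claims. OS, PFS and ORR testing is untouched.

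**What to change.** In Protocol 8.4.5.2, and in the matching SAP text if it does not already do so:

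- Base any statement that a marker is predictive on models fitted to both arms with treatment, marker and treatment-by-marker interaction: logistic for response, and Cox stratified by the two randomization factors for PFS and OS.
- Report the nivolumab-versus-chemotherapy odds ratio or hazard ratio with 95% CI within each marker level, together with the interaction estimate and its CI.
- Label the marker-outcome associations already planned as prognostic or association only.

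The same edit could reconcile the analysis set: Protocol 8.2 defines biomarker subjects among those treated, whereas 8.4.5.2 uses those randomized.

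The cost is wording and one model term per endpoint, using data already collected, with no alpha spent. The price is precision. With power of about 21-62% even for OR 3 against 1, a non-significant interaction must not be read as evidence that a marker is not predictive, and fewer markers will earn the label.

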8.4.6 Outcomes Research Analyses

LCSS questionnaire complete rate, defined as the proportion of questionnaires actually received out of the expected number (ie, the number of subjects still on treatment or in follow-up), will be calculated and summarized at each assessment point.

Baseline and change from baseline of the average symptom burden index score at each assessment point will be summarized using descriptive statistics.

Subject's overall health state on a visual analog scale (EQ-VAS) at each assessment time point will be summarized using descriptive statistics. Proportion of subjects reporting problems for the 5 EQ-5D dimensions at each assessment time point will be summarized by level of problem.

Summary statistics will be calculated for the population preference-based health state utility score (EQ-5D Index).

8.4.7 Other Analyses

Methodology for exploratory analyses including immunogenicity, other HRQoL assessments (PRO), and healthcare resource utilization is described in the statistical analysis plan.

8.5 Interim Analyses

No formal analysis for OS will be performed for this study.

A DMC will have access to periodic unblinded interim reports of efficacy and safety to allow a risk/benefit assessment. No formal test will be performed and the study will not stop for superiority. Details will be included in the DMC charter.

9 STUDY MANAGEMENT

9.1 Compliance

9.1.1 Compliance with the Protocol and Protocol Revisions

The study shall be conducted as described in this approved protocol. All revisions to the protocol must be discussed with, and be prepared by, BMS. The investigator should not implement any deviation or change to the protocol without prior review and documented approval/favorable opinion from the IRB/IEC of an amendment, except where necessary to eliminate an immediate hazard(s) to study subjects.

If a deviation or change to a protocol is implemented to eliminate an immediate hazard(s) prior to obtaining IRB/IEC approval/favorable opinion, as soon as possible the deviation or change will be submitted to:

- IRB/IEC for review and approval/favorable opinion
- BMS
- Regulatory Authority(ies), if required by local regulations

Documentation of approval signed by the chairperson or designee of the IRB(s)/IEC(s) must be sent to BMS.

If an amendment substantially alters the study design or increases the potential risk to the subject: (1) the consent form must be revised and submitted to the IRB(s)/IEC(s) for review and approval/favorable opinion; (2) the revised form must be used to obtain consent from subjects currently enrolled in the study if they are affected by the amendment; and (3) the new form must be used to obtain consent from new subjects prior to enrollment.

If the revision is done via an administrative letter, investigators must inform their IRB(s)/IEC(s).

9.1.2 Monitoring

BMS representatives will review data centrally to identify potential issues to determine a schedule of on-site visits for targeted review of study records.

Representatives of BMS must be allowed to visit all study site locations periodically to assess the data quality and study integrity. On site they will review study records and directly compare them with source documents, discuss the conduct of the study with the investigator, and verify that the facilities remain acceptable.

In addition, the study may be evaluated by BMS internal auditors and government inspectors who must be allowed access to CRFs, source documents, other study files, and study facilities. BMS audit reports will be kept confidential.

The investigator must notify BMS promptly of any inspections scheduled by regulatory authorities, and promptly forward copies of inspection reports to BMS.

9.1.2.1 Source Documentation

The Investigator is responsible for ensuring that the source data are accurate, legible, contemporaneous, original and attributable, whether the data are hand-written on paper or entered electronically. If source data are created (first entered), modified, maintained, archived, retrieved, or transmitted electronically via computerized systems (and/or any other kind of electronic devices) as part of regulated clinical trial activities, such systems must be compliant with all applicable laws and regulations governing use of electronic records and/or electronic signatures. Such systems may include, but are not limited to, electronic medical/health records (EMRs/EHRs), AE tracking/reporting, protocol required assessments, and/or drug accountability records).

When paper records from such systems are used in place of electronic format to perform regulated activities, such paper records should be certified copies. A certified copy consists of a copy of original information that has been verified, as indicated by a dated signature, as an exact copy having all of the same attributes and information as the original.

9.1.3 Investigational Site Training

Bristol-Myers Squibb will provide quality investigational staff training prior to study initiation. Training topics will include but are not limited to: GCP, AE reporting, study details and procedure, electronic CRFs, study documentation, informed consent, and enrollment of WOCBP.

9.2 Records

9.2.1 Records Retention

The investigator must retain all study records and source documents for the maximum period required by applicable regulations and guidelines, or institution procedures, or for the period specified by BMS, whichever is longer. The investigator must contact BMS prior to destroying any records associated with the study.

BMS will notify the investigator when the study records are no longer needed.

If the investigator withdraws from the study (eg, relocation, retirement), the records shall be transferred to a mutually agreed upon designee (eg, another investigator, IRB). Notice of such transfer will be given in writing to BMS.

9.2.2 Study Drug Records

It is the responsibility of the investigator to ensure that a current disposition record of study drug (inventoried and dispensed) is maintained at the study site to include investigational product. Records or logs must comply with applicable regulations and guidelines and should include:

- amount received and placed in storage area
- amount currently in storage area
- label identification number or batch number
- amount dispensed to and returned by each subject, including unique subject identifiers
- amount transferred to another area/site for dispensing or storage
- nonstudy disposition (eg, lost, wasted)
- amount destroyed at study site, if applicable
- amount returned to BMS
- retain samples for bioavailability/bioequivalence, if applicable
- dates and initials of person responsible for Investigational Product dispensing/accountability, as per the Delegation of Authority Form.

BMS will provide forms to facilitate inventory control if the investigational site does not have an established system that meets these requirements.

9.2.3 Case Report Forms

An investigator is required to prepare and maintain adequate and accurate case histories designed to record all observations and other data pertinent to the investigation on each individual treated or entered as a control in the investigation. Data that are derived from source documents and reported on the CRF must be consistent with the source documents or the discrepancies must be explained. Additional clinical information may be collected and analyzed in an effort to enhance understanding of product safety. CRFs may be requested for AEs and/or laboratory abnormalities that are reported or identified during the course of the study.

For sites using the BMS electronic data capture tool, electronic CRFs will be prepared for all data collection fields except for fields specific to SAEs and pregnancy, which will be reported on the paper or electronic SAE form and Pregnancy Surveillance form, respectively. Spaces may be left blank only in those circumstances permitted by study-specific CRF completion guidelines provided by BMS.

The confidentiality of records that could identify subjects must be protected, respecting the privacy and confidentiality rules in accordance with the applicable regulatory requirement(s).

The investigator will maintain a signature sheet to document signatures and initials of all persons authorized to make entries and/or corrections on CRFs.

The completed CRF, including any paper or electronic SAE/pregnancy CRFs, must be promptly reviewed, signed, and dated by the investigator or qualified physician who is a subinvestigator and who is delegated this task on the Delegation of Authority Form. For electronic CRFs, review and approval/signature is completed electronically through the BMS electronic data capture tool. The investigator must retain a copy of the CRFs including records of the changes and corrections.

Each individual electronically signing electronic CRFs must meet BMS training requirements and must only access the BMS electronic data capture tool using the unique user account provided by BMS. User accounts are not to be shared or reassigned to other individuals.

